4.1 Pre-registration

NOTE: Patients who are only pre-registered must not begin treatment.

To proceed to randomization, patients must have centralized immunophenotyping performed by the ECOG-ACRIN Leukemia Translational Studies Laboratory.

4.1.1 Protocol Number

4.1.2 Investigator Identification

4.1.2.1 Institution and affiliate name (Institution CTEP ID)

4.1.2.2 Investigator's name (NCI number)

4.1.2.3 Cooperative Group Credit

4.1.2.4 Credit Investigator

4.1.2.5 Protocol specific contact information

4.1.3 Patient Identification

4.1.3.1 Patient's initials (first and last)

4.1.3.2 Patient's Hospital ID and/or Social Security number

4.1.3.3 Patient demographics

4.1.3.3.1 Gender

4.1.3.3.2 Birth date

4.1.3.3.3 Race

4.1.3.3.4 Ethnicity

4.1.3.3.5 Nine-digit ZIP code

4.1.3.3.6 Method of payment

4.1.3.3.7 Country of residence

4.1.4 Eligibility Verification

Patients must meet all of the eligibility requirements listed in Section [3.1](#).

4.1.5 Additional Requirements

4.1.5.1 Patients must provide a signed and dated, written informed consent form.

4.1.5.2 Bone marrow and peripheral blood specimens **must be submitted** at pre-registration for centralized immunophenotyping.

NOTE: Copies of the consent are not collected by the ECOG-ACRIN Operations Office. However the ECOG-ACRIN Leukemia Translational Studies Laboratory (LTSL) requires institutions to submit a copy of the E2906 consent and a copy of the HIPAA Authorization form.

Rev. 7/14	4.2	Step 1: Randomization to Induction (ARMS A or B)
	4.2.1	Protocol Number
	4.2.2	Investigator Identification
Rev. 2/13	4.2.2.1	[Deleted in Addendum #4]
	4.2.2.2	Investigator's name (NCI number)
	4.2.2.3	Cooperative Group Credit
	4.2.2.4	Credit Investigator
	4.2.2.5	Protocol specific contact information
	4.2.3	Patient Identification
	4.2.3.1	Patient's initials (first and last)
	4.2.3.2	Patient's Hospital ID and/or Social Security number
	4.2.3.3	Patient demographics
	4.2.3.3.1	Gender
	4.2.3.3.2	Birth date
	4.2.3.3.3	Race
	4.2.3.3.4	Ethnicity
	4.2.3.3.5	Nine-digit ZIP code
	4.2.3.3.6	Method of payment
	4.2.3.3.7	Country of residence
	4.2.4	Eligibility Verification
		
Patients must meet all of the eligibility requirements listed in Section 3. An eligibility checklist has been appended to the protocol. A confirmation of registration will be forwarded by the ECOG-ACRIN Operations Office - Boston.

Rev. 2/12	4.2.5	Stratification
		
• Age 60-69 vs. \geq 70 years• [Deleted in Addendum #3]• Therapy-related AML (any prior treatment with chemotherapy or radiation therapy for another malignancy)• Antecedent Hematological Disorders (AHD) (prior diagnosis of MDS, myeloproliferative disorder or other hematologic disorder)
Rev. 2/12, 12/13	4.2.6	Additional Requirements (1 st Randomization)
	4.2.6.1	Patients must provide a signed and dated, written informed consent form.
	4.2.6.2	Baseline and follow-up peripheral blood and buccal swabs are to be submitted as outlined in Section 10 for banking, per patient consent.

Rev. 12/13

4.2.6.3 Baseline and follow-up karyotypes must be submitted for central review as outlined in Section [10](#).

NOTE: Specimens submitted for mandatory central reviews will also be used for the optional correlative studies indicated in Section [10](#) per patient consent.

NOTE: ECOG-ACRIN requires that biological samples submitted from patients be entered and tracked via the online ECOG-ACRIN Sample Tracking System (STS).

Rev. 2/12

NOTE: Institutions outside of the United States and Canada must confer with the receiving laboratory and the ECOG-ACRIN Operations Office - Boston regarding logistics for submission of fresh or frozen samples.

4.3 Step 2: Registration to Consolidation (ARMS C or D)

All patients must register to step 2. Patients who are proceeding to transplant and are not receiving consolidation therapy may proceed immediately to Registration to Transplant (Step 3).

4.3.1 Protocol Number

4.3.2 Investigator Identification

4.3.2.1 Institution and affiliate name (Institution CTEP ID)

4.3.2.2 Investigator's name (NCI number)

4.3.2.3 Cooperative Group Credit

4.3.2.4 Credit Investigator

4.3.2.5 Protocol specific contact information

4.3.3 Patient Identification

4.3.3.1 Patient's initials (first and last)

4.3.3.2 Patient's Hospital ID and/or Social Security number

4.3.3.3 Patient demographics

4.3.3.3.1 Gender

4.3.3.3.2 Birth date

4.3.3.3.3 Race

4.3.3.3.4 Ethnicity

4.3.3.3.5 Nine-digit ZIP code

4.3.3.3.6 Method of payment

4.3.3.3.7 Country of residence

4.3.4 Eligibility Verification

Patients must meet all of the eligibility requirements listed in Section [3](#). An eligibility checklist has been appended to the protocol. A

		confirmation of registration will be forwarded by the ECOG-ACRIN Operations Office - Boston.
	4.3.5	Classification
		• Induction Treatment (Arm A vs Arm B)
Rev. 7/14	4.3.6	Additional Requirements (Randomization)
Rev. 12/13	4.3.6.1	Follow-up karyotypes, smears, bone marrow and peripheral blood must be submitted for central review as outlined in Section 10 .
Rev. 2/12 Rev. 12/13	4.3.6.2	Follow-up peripheral blood is to be submitted as outlined in Section 10 for banking, per patient consent.
	NOTE:	Specimens submitted for central review will also be used for the optional correlative studies outlined in Section 10 per patient consent.
Rev. 12/13	NOTE:	ECOG-ACRIN requires that all biological samples submitted be entered and tracked via the online ECOG-ACRIN Sample Tracking System (STS).
4.4	Step 3: 2nd Randomization-Maintenance (Arms E or F), or Registration to Transplant (Arm G)	
	4.4.1	Protocol Number
	4.4.2	Investigator Identification
	4.4.2.1	Institution and affiliate name (Institution CTEP ID)
	4.4.2.2	Investigator's name (NCI number)
	4.4.2.3	Cooperative Group Credit
	4.4.2.4	Credit Investigator
	4.4.2.5	Protocol specific contact information
	4.4.3	Patient Identification
	4.4.3.1	Patient's initials (first and last)
	4.4.3.2	Patient's Hospital ID and/or Social Security number
	4.4.3.3	Patient demographics
	4.4.3.3.1	Gender
	4.4.3.3.2	Birth date
	4.4.3.3.3	Race
	4.4.3.3.4	Ethnicity
	4.4.3.3.5	Nine-digit ZIP code
	4.4.3.3.6	Method of payment
	4.4.3.3.7	Country of residence

	4.4.4	Eligibility Verification
		
Patients must meet all of the eligibility requirements listed in Section 3. An eligibility checklist has been appended to the protocol. A confirmation of registration will be forwarded by the ECOG-ACRIN Operations Office - Boston.

Rev. 2/13	4.4.5	Stratification and Classification Factors
	4.4.5.1	Classification for Registration to Transplant
		
• [Deleted in Addendum #4]• Transplant donor Identified: HLA-Identical Sibling (6/6) or Matched Unrelated Donor (10/10)
Rev. 2/13		
NOTE: For matched donors – will allow select 1 antigen mismatched sibling donors and unrelated donors in accordance with site institutional standard, as long as matched at HLA-A, HLB, HLA-C, and DRB1, and with advanced discussion/approval by the Study Chair and the BMT co-chair.

Rev. 7/14	4.4.5.2	Stratification for Randomization to Maintenance
		
• Age 60-69 vs. \geq 70 years• Cytogenetics unfavorable vs. “other”• Induction Treatment (Arm A vs. B)
Rev. 12/13	4.4.6	Additional Requirements (2 nd Randomization)
	4.4.6.1	Follow-up karyotypes, smears, bone marrow and peripheral blood must be submitted for central review as outlined in Section 10 .
Rev. 2/12, 12/13	4.4.6.2	Follow-up peripheral blood is to be submitted as outlined in Section 10 for banking, per patient consent.
		
NOTE: Specimens submitted for central review will also be used for the optional correlative studies outlined in Section 10 per patient consent.

Rev. 12/13		
NOTE: ECOG-ACRIN requires that all biological samples submitted from patients be entered and tracked via the online ECOG-ACRIN Sample Tracking System (STS).

		
NOTE: FACT (Foundation for the Accreditation of Cellular Therapy) credentialing certificate must be submitted to the CTSU Patient Registrar at [name] at time of patient registration to Arm G.

Rev. 7/14	4.5	Instructions for Patients who Do Not Start Assigned Protocol Treatment
		
If a patient does not receive any assigned protocol treatment, baseline and follow-up data will still be collected and must be submitted according to the instructions in the E2906 Forms Packet. Document the reason for not starting

protocol treatment on the Off Treatment form. Also report the date and type of the first non-protocol treatment that the patient receives.

4.6 Investigator's Drug Brochure and Safety Alerts

A copy of the Investigator's Drug Brochure (IDB) for Clofarabine and the drug package insert for Decitabine are available for download from the ECOG webpage. The IDB and drug package insert provide relevant and current scientific information about the drug products. The IDB and drug package insert should be submitted to your IRB/EC according to GCP regulations. The Clofarabine IDB, the Decitabine drug package insert and any correspondence to the Institutional Review Board (IRB)/Ethics Committee (EC) should be kept in the E2906 regulatory files.

Should any SAE report on this study qualify as a safety alert report requiring expedited reporting, the SAE report will be sent by the sponsors to regulatory authorities globally (including the FDA) and ECOG-ACRIN. If applicable, ECOG-ACRIN will disseminate these safety alert reports to all participating investigators in the bimonthly group mailings. These reports should be forwarded to your IRB/EC within 90 days of receipt for review. Reporting instructions are provided with each safety alert. These safety alerts and any correspondence to your IRB/EC should be maintained in your E2906 study file.

4.7 IND Status

The use of Clofarabine and Decitabine in this trial is classified as "off-label" or unapproved use of FDA-approved drugs. When a drug or combination of drugs is used in an off-label manner as part of a clinical trial, it is, by rule, considered as an investigational treatment regimen. However, while these treatment regimens are not approved by the FDA, their use is exempt from the requirements for an IND to conduct this study as defined under Title 21 CFR 312.2(b) of the codified FDA regulations

5. Treatment Plan

5.1 Induction Therapy and Premedications

NOTE: Doses to be calculated using actual body weight.

5.1.1 Initial Considerations

Patients should begin treatment with Allopurinol 300 mg/day orally. Reversible abnormalities of renal or metabolic function should be treated aggressively and corrected prior to institution of therapy. Immediate measures to diagnose and begin treatment of infections should be instituted prior to induction therapy.

Patients should be adequately hydrated with NS or equivalent and achieve a target urine output \geq 100ml/hour average prior to starting induction therapy. This should be maintained throughout the first 5-7 days of induction therapy, with adjustments as clinically indicated to maintain volume status and prevent volume overload. Appropriate monitoring for evidence of tumor lysis should also be performed for the first 3-5 days of induction therapy (e.g. measurement of K^+ , PO_4^{3-} , serum creatinine, calcium and uric acid q 8-12 hours)

Patients with high circulating blast cell counts $> 50,000/\mu l$, should be given hydroxyurea 750 mg/ m^2 (or more) orally every 6-12 hours until the absolute blast count falls $< 50,000/\mu l$.

NOTE: Patients who present with a clinically significant increase in the peripheral blast count may receive hydroxyurea prior to the start of induction. A suggested dose is 1 to 2 gm po every six hours, at the discretion of the physician. The hydroxyurea must be discontinued prior to administration of induction. Hydroxurea suggested minimum 500–1000 mg PO twice a day. Suggested maximum dose is not to exceed 4,000 mg twice a day.

NOTE: Patients with M4 or M5 disease and who have CNS signs or symptoms should have a lumbar puncture once blasts have cleared from the peripheral blood smear.

NOTE: Up to two courses of induction therapy are permitted to achieve marrow aplasia. Patients who have not achieved CR, CRi, or a morphologic leukemia-free state after the second cycle of induction are taken off study and further treatment is at the discretion of the investigator.

NOTE: Allopurinol 300 mg daily or the dose adjusted for renal insufficiency should be administered prior to starting induction through the completion of the cytarabine infusion during induction.

Patients will be randomized to one of the following induction therapy arms:

5.1.2 **ARM A** Standard Therapy with "7&3 schedule"

Daunorubicin 60 mg/ m^2 /day by 10 - 15 minute intravenous infusion for 3 days (days 1, 2, and 3).

Cytarabine 100 mg/m²/day by 24 hour continuous intravenous infusion for 7 days (days 1-7).

NOTE: There are no dose modifications during initial induction.

Dexamethasone 10 mg IV QD (or equivalent) and Ondansetron 16 mg IV, or PO, or equivalent, is suggested as an anti-emetic.

Rev. 2/12

Patients with residual AML by morphologic review or who do not achieve an aplastic BM on day 12-14 (i.e. < 5% blasts and < 20% cellularity or markedly/moderately hypocellular) are eligible to receive a 2nd cycle of induction therapy with the same dose & schedule of daunorubicin & cytarabine beginning no sooner than day 14.

5.1.3

ARM B Clofarabine

Clofarabine 30mg/m²/day IV by 1 hour infusion QD x 5 days

Dexamethasone 10 mg IV QD (or equivalent) and Ondansetron 16 mg IV, or PO, or equivalent, is suggested as an anti-emetic.

Patients with residual AML or who do not achieve an aplastic BM on day 12-14 (i.e. < 5% blasts and < 20% cellularity or markedly/moderately hypocellular) are eligible to receive a 2nd cycle of induction therapy with clofarabine at the **lower ‘consolidation’ dose of 20mg/m²/day IV QD x 5 days**.

The creatinine must be measured daily during the first cycle of clofarabine treatment. Dose adjustments for an increase in serum creatinine > grade I during clofarabine treatment will be according to Dose Modification, Section [5.4.4](#).

Rev. 2/12

NOTE: Dose adjustments for the first induction cycle of clofarabine will follow Section [5.4.4](#).

The 2nd cycle of induction with clofarabine must not commence sooner than day 21 and no later than day 56, and must be withheld until creatinine, AST & total bilirubin are ≤ grade I (See Section [5.4.4](#) for dose modifications).

5.1.4

Restaging

Rev. 2/13

A restaging BM will be performed on day 12 -14 (+/- 1 day) to determine whether patients have achieved an aplastic BM (i.e. < 5% blasts and < 20% cellularity, or markedly/moderately hypocellular). Patients who achieve an aplastic BM should start GM-CSF or G-CSF, or pegfilgrastim (unless contraindicated). Those with residual leukemia or who do not achieve an aplastic or markedly/moderately hypocellular BM are eligible for re-induction with a 2nd cycle of chemotherapy as noted above.

Rev. 2/13

A repeat BM for outcome will be performed between day 28 – day 56 from the start of initial therapy after 1st or 2nd induction either when the ANC is > 1000 and platelets > 100,000, or if there is evidence of delayed hematologic recovery and it is felt that the ANC will not reach 1000 or the platelet count > 100,000, to document response to induction therapy. Those with an HLA-matched donor identified who achieve a “morphologic leukemia-free state” on or before day 56 may

proceed to allogeneic transplantation if medically appropriate and per physician discretion. Patients proceeding to transplant are allowed up to 1 cycle of consolidation before the transplant. See Sections [5.1.6](#) and [5.1.7](#).

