5.1.5 Criteria for Second Induction Cycle

A bone marrow aspirate and biopsy is performed on day 12-14 (\pm 1 day), i.e. 5-7 days after the completion of the cytarabine infusion or 7-9 days after completion of clofarabine treatment. The decision to administer a second induction cycle is based on the following criteria:

NOTE: Patients undergoing 2nd induction who do not achieve complete response by day 56 of the start of re-induction will be taken off protocol treatment.

Rev. 2/12,
2/13

5.1.5.1 If the marrow cellularity is judged to be greater than 20%, or not markedly/moderately hypocellular on the marrow biopsy, or with > 5% blasts, or the bone marrow is indeterminate, then repeat induction is indicated.

If the marrow cellularity is less than markedly hypocellular, or moderately hypocellular, or there are persistent circulating blasts, then the patient's status should be followed with a repeat marrow assessment within 5 to 7 days.

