6.2 Complete Remission incomplete (CRI)

All the same response criteria in peripheral blood and bone marrow as CR with the exception that there is incomplete platelet recovery (platelets $> 50 \times 10^9 / L$ independent of platelet transfusions) over a period of observation without evidence of ongoing platelet recovery and no sooner than day 35 after the preceding cycle of treatment.

Rev. 8/13

6.2.1 Patients who achieve criteria for CR or CRI and who have recovered from the effects of therapy but who have **< 20% cellularity in BM** will be deemed a "Hypocellular CR/CRI" and will be allowed to continue protocol therapy at the discretion of the Investigator and after discussion with the Study Chair as long as they meet other eligibility criteria for Step 2

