- 2 It is required that complete blood counts be obtained every 4 weeks for the first twenty-four months after the conclusion of consolidation therapy. Complete blood counts should be obtained every three months in the third year. The frequency in subsequent years is at the discretion of the investigator.
- 3 During the administration of daunorubicin or high-dose cytarabine the serum creatinine and total bilirubin are required daily to adjust dose of medications. After the administration of chemotherapy the values must be determined and reported at least weekly or more frequently as clinically indicated.
- 4 A bone marrow is required on day 12-14 (+/- 1 day) to assess whether the patient has achieved an aplastic BM and will receive GM-CSF or G-CSF or a repeat course of induction. Subsequent marrows until recovery of peripheral blood counts are at the discretion of the treating physician. An outcome BM must be performed no sooner than day 28 and no later than day 56 to determine response to induction therapy at the time of recovery of ANC to >1000 & platelets (>100,000) or if the patients is suspected to have residual AML, or if no further recovery is expected (e.g. plateau in platelet recovery).
- 5 If the cardiac ejection fraction cannot be obtained due to weekend or holiday then patients may be enrolled provided there are no clinical signs or there is no history of significant cardiovascular disease and a measurement of cardiac ejection fraction will be performed within 5 days of study enrollment.

6 Prior to each dose of cytarabine during consolidation for patients randomized to Arms A and C.

Rev. 2/13 7 The Cardiac Ejection Fraction must be measured prior to Induction. For patients on Arm A, a repeat measurement is recommended before receiving re-induction (if indicated). Repeat measurement prior to Consolidation Cycle 1 (Arms C & D) is recommended per institutional guidelines and as clinically indicated. **For patients who proceed to Arm G (Allogeneic stem cell transplantation) a repeat measurement of Cardiac Ejection Fraction must be performed after recovery from last cycle of chemotherapy and prior to start of transplant conditioning regimen**

Rev. 2/12 8 Routine bone marrow aspirate and biopsy is required every 3 months during maintenance and observation (Arms E and F) for first 24 months.

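### The outcome marrow after re-induction is timed from initial therapy in Section 5.1.4, but the response deadline in Section 5.1.5 runs from re-induction, and the plan names no clock for the induction CR rate

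*Combined protocol and SAP*

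**What the plan says.** - **Section 5.1.4 (Restaging)** says: "A repeat BM for outcome will be performed between day 28 – day 56 from the start of initial therapy", and applies this window after a first or a second induction. Re-induced patients are therefore expressly covered, and their clock starts with the first cycle.
- **Section 5.1.5 (Criteria for Second Induction Cycle)** addresses the same patients: those "who do not achieve complete response by day 56 of the start of re-induction will be taken off protocol treatment". Their clock starts with the second cycle.
- **Section 7.1, footnote 4** says: "An outcome BM must be performed no sooner than day 28 and no later than day 56 to determine response to induction therapy". It names no origin. Section 5.6.1 also calls for a repeat marrow at day 56 in patients without count recovery, again with no origin.
- **Sections 5.1.2 and 5.1.3** set when the second cycle may start. Arm A may restart "beginning no sooner than day 14", with no latest day given. For Arm B: "The 2nd cycle of induction with clofarabine must not commence sooner than day 21 and no later than day 56".
- **Section 6.2** allows CRi to be called "no sooner than day 35 after the preceding cycle of treatment", without saying whether this counts from the first or the last day of that cycle.
- **Section 9.4** tests the induction CR rate for non-inferiority with a 10-point margin and monitors it for inferiority. It names no clock and no time limit for the endpoint, and does not say whether CRi counts as CR. Section 6 sets no time limit for CR either.

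**The concern.** A re-induced patient cannot be on both clocks. A site following Section 5.1.4 and a site following Section 5.1.5 could document response in the same patient on different dates, and a remission that appears between the two deadlines could be recorded by one site and missed by the other.

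The clash does not fall equally on the arms. Arm B may not restart until a week after Arm A's earliest restart, and its permitted start window runs to day 56 itself. If the initial-therapy clock governed scoring, Arm B would have less time for counts to recover and for a qualifying marrow. At stake are the CR non-inferiority test, the interim rule on CR, and the documentation of response on which entry to consolidation or transplant depends.

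**Working it through.** **The plan's own CR figure.** Section 9.4 states 85% power with 747 patients, CR 40% on standard therapy, clofarabine better by 1 point, a margin of 10 points and one-sided 0.025. Assuming 1:1 allocation (Section 9 states no ratio), there are 373.5 per arm.

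- SE = √[(0.40 × 0.60 + 0.41 × 0.59) / 373.5] = 0.0359
- Fixed-sample power = Φ((0.10 + 0.01)/0.0359 − 1.96) = 86.5%
- With a final critical value of about 2.05, simulated for truncated O'Brien-Fleming spending at the five CR looks: 84.4%

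The stated 85% is reproduced and is not in dispute. What is missing is the rule for when a remission counts towards the rate being tested.

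**The two clocks.** Let s be the study day on which re-induction starts, counted from initial therapy. Under Section 5.1.4 the time left after re-induction starts is 56 − s. Under Section 5.1.5 it is always 56 days, ending on study day s + 56.

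| Re-induction start (s) | Permitted in | Days left, Section 5.1.4 | Last study day, Section 5.1.5 |
|---|---|---|---|
| 14 | Arm A, earliest | 56 − 14 = 42 | 14 + 56 = 70 |
| 21 | Arm B, earliest | 56 − 21 = 35 | 21 + 56 = 77 |
| 28 | both | 28 | 84 |
| 42 | both | 14 | 98 |
| 56 | Arm B, latest | 0 | 112 |

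Arm A has no stated latest day, so an Arm A restart on day 28 or day 42 loses as much time as one in Arm B. The between-arm difference that the text itself fixes is the one at the earliest starts: 42 − 35 = 7 days.

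The last row shows that the rules cannot all be followed. A second clofarabine cycle begun on day 56 is permitted, yet the outcome marrow after that cycle would be due on the day the cycle begins.

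**CRi.** The earliest day depends on how Section 6.2 is counted.

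- From day 1 of re-induction: 14 + 35 = day 49 in Arm A and 21 + 35 = day 56 in Arm B.
- From the last dose (day 7 of the cycle in Arm A, day 5 in Arm B): 14 + 6 + 35 = day 55 and 21 + 4 + 35 = day 60.

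The documents do not choose between these counts.

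**Do other sections settle the origin?** No. The quality-of-life timings in Sections 6.7 and 7.1 describe the outcome marrow as day 35 to 56, again unanchored. Sections 5.4.4.1 and 5.4.5, by contrast, count explicitly from day 1 of a treatment cycle, so the protocol names an origin in some places and not here.

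**The case against.** The strongest reply is that Section 5.1.4 schedules a marrow and does not define an endpoint. Neither Section 6 nor Section 9.4 puts a day-56 limit on CR. Section 5.6.1 keeps patients without recovery under at least weekly blood counts until recovery, refractory disease or death. Section 5.7 follows every patient for response until progression, including those who stop protocol therapy early. Late remissions are therefore still looked for, and nothing makes them non-responses. This stands. A reader might infer that the CR comparison is biased against clofarabine; the documents do not support that, because the disadvantage arises only if the scheduling window is also used for scoring.

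It can also be said that Section 5.1.5 sets an off-treatment deadline, so the two sections govern different things. That is literally so, but CR requires a marrow (Section 6.1.2), so a deadline for complete response works in practice as a deadline for the marrow. And Section 5.1.4 expressly extends its own clock to the second cycle.

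A reader might also conclude that Arm B patients re-induced after day 21 can never be scored CRi. That holds only under the Section 5.1.4 clock with day 35 counted from the start of re-induction, and it bears on the CR test only if CRi counts as CR. The text settles none of these.

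Finally, Section 9.5 records that Step 1 accrual was suspended after 727 patients because of overall survival. Rewording cannot change how those patients were assessed, and stopping induction randomisation on CR is no longer a live decision. The analysis definition can still be fixed.

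**Conclusion.** The inconsistency holds and is wrong as written. Sections 5.1.3, 5.1.4 and 5.1.5 cannot all be followed for some re-induced patients, and footnote 4 and Section 5.6.1 do not resolve it. Under the initial-therapy clock the time left at the earliest permitted starts is 42 days in Arm A and 35 in Arm B, falling to 0 for the latest Arm B start. Under the re-induction clock it is 56 days in both.

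The consequence is conditional. If the Section 5.1.4 window were applied to scoring, it could disadvantage Arm B in a formally tested secondary endpoint. No loss in CR rate or power should be inferred from this: the documents give no re-induction rate, no late-remission rate and no distribution of restart days, and Arm A patients who restart late would lose time too. Overall survival runs from randomisation to death and does not depend on either clock.

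**What to change.** 1. Reconcile Sections 5.1.3, 5.1.4, 5.1.5, 5.6.1 and 6.2 and footnote 4 of Section 7.1 to one stated time origin. Which clinical rule is right is for the study team; no view is taken here.
2. In Section 9.4, name one time origin for the induction CR analysis and apply it identically to both arms. State whether remissions documented after day 56 from initial therapy count, and whether CRi counts as CR.
3. Add a sensitivity analysis of the CR difference under the other clock, and tabulate re-induction start days by arm so that readers can see how much the choice matters.

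The cost is protocol wording, one endpoint definition, one sensitivity analysis and one table. It requires no change to sample size or to the primary analysis.
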